4: Vital signs to include temperature, pulse, respirations, blood pressure, weight, and height (screening only) and ECOG performance status. Patients will be monitored before, during and after the durvalumab infusion with assessment of vital signs. Patients are monitored (pulse rate, blood pressure) every 30 minutes (- 5 minutes/+ 10 minutes), during the infusion period (including times where infusion rate is slowed or temporarily stopped).

5: CBC with differential and platelet to include: WBC, ANC, Hgb, Hct, PLT. CMP to include sodium, potassium, chloride, creatinine, blood urea nitrogen; liver function tests (LFTs) to include AST, ALT, total bilirubin, alkaline phosphatase. Thyroid Function testing should be performed at

screening, at start of consolidation durvalumab, then every 3 cycles during consolidation durvalumab. TSH will be obtained. T4 and T3 including free versus total testing is at the discretion of the site investigator.

6: For women of childbearing potential (WOCBP): urine or serum  $\beta$ hCG will be done at screening and within 24 hrs of 1st dose of study drug. During treatment with consolidation durvalumab, a pregnancy test should be performed every 4 weeks. If a urine test is done and it is positive or cannot be confirmed as negative, a serum pregnancy test will be required.

7: Tumor assessments to be performed at (1) screening (PET scan may be within 42 days prior to C1D1) (2) within 0-24 days after completion of chemoradiation/prior to C1D1 of consolidation durvalumab, then every 3 months (about every 3 cycles/ $\pm$  7 business days) during consolidation durvalumab. Screening tumor assessment will consist of evaluation by CT scans of chest (contrast enhanced), PET scan, and contrast-enhanced MRI or CT of the brain. Response assessment imaging will include CT scans of chest, abdomen, and pelvis (contrast enhanced). MRI or CT brain or PET scan after screening should be performed as clinically indicated. Imaging selected for each subject should remain the same throughout the study. Tumor imaging at treatment discontinuation/D30 safety follow up visit is at discretion of site investigator. If tumor assessments are available for subjects who have not yet experienced progressive disease (PD) at the time treatment is discontinued, the follow-up tumor evaluations will be documented in the eCRF until PD or death is confirmed, or until another treatment is initiated. A window of 7 days may be applied to obtain scans.

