12: After the D100 safety visit, subjects who discontinue treatment for any reason without documented disease progression will be followed for disease progression every 3 months up to 12 months after initiation of consolidation durvalumab. Once disease progression is documented, subjects will enter a survival follow up period every 6 months for 1 year from the time of documented progression or until 1 year after initiation of consolidation durvalumab. Follow up may be accomplished via clinic visit, phone call, or other avenues as appropriate. A window of  $\pm$  14 days will be applied to follow up.

13: If screening (baseline) CBC and CMP were performed within 7 days of Day 1 of treatment, these do not need to be repeated. All laboratory assessments should be done prior to treatment.

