#### 9.8.8 Progression Free Survival

12-month progression-free survival will be measured using imaging prior to C1D1 consolidation durvalumab (between 1-42 days after completion of chemoradiation) as baseline. This timepoint is selected in order to compare with the PACIFIC trial 12-month progression-free survival as historical control. 12-month PFS will be defined as the time from the date of CT prior to beginning consolidation radiation until the date of objective disease progression or death (by any cause in the absence of progression), as measured for the 12-month period after initiation of consolidation durvalumab.

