## 12.6 Data Analysis Plans

### 12.6.1 Analysis Plans for Primary Objective

The progression-free survival analyses will be performed considering the risk of dying from another cause before experiencing progression related events using the competing risk egression method (de Glas et al., 2016). Cumulative incidence functions will be displayed and summarized for the median time to progression as well as percentage of progression patients at 12, 18, and 24 months. In addition, competing risk regression will be used to estimate sub distribution hazard ratios of the study arm versus historical control arm and 95% confidence intervals, adjusted for patient demographic, clinical, pathological, and tumor related factors. To compare the overall survival between groups, Kaplan-Meier survival curves will be displayed and summarized. Survival curves will be statistically compared using the log-rank test. If the proportional hazards assumption is met, survival curves will also be compared using proportional Cox regression, adjusting for risk factors.

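### Section 12.6.1 promises 18- and 24-month progression percentages, but scheduled progression follow-up ends 12 months after consolidation starts, and the sample size assumes longer follow-up than that

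*Combined protocol and SAP*

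**What the plan says.** Section 12.6.1 summarises the cumulative incidence functions by a median and by the "percentage of progression patients at 12, 18, and 24 months".

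The follow-up rules are elsewhere:

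- **Study Calendar, footnote 12.** Patients who leave treatment without progression are "followed for disease progression every 3 months up to 12 months after initiation of consolidation durvalumab". This follow-up begins after the day-100 safety visit. For patients who have progressed, the rule is: "survival follow up period every 6 months for 1 year from the time of documented progression or until 1 year after initiation of consolidation durvalumab".
- **Section 9.8.8.** PFS is defined "as measured for the 12-month period after initiation of consolidation durvalumab".
- **Study Calendar, footnote 7.** Scans are scheduled "within 0-24 days after completion of chemoradiation/prior to C1D1 of consolidation durvalumab, then every 3 months" while consolidation lasts, which is up to 12 four-week cycles. Later evaluations are recorded until progression, death or a new treatment, but under a condition: "If tumor assessments are available for subjects who have not yet experienced progressive disease (PD) at the time treatment is discontinued". No schedule is given for them.
- **Study Calendar table.** The long-term follow-up column marks CT of chest, abdomen and pelvis.
- **Section 12.3.** The sample size of 49 assumes 18 months of accrual and a further 12 months of follow-up, so 12 to 30 months per patient. The synopsis estimates a 36-month study.

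**The concern.** A cumulative incidence at 18 or 24 months needs patients still under planned observation at those times. Footnote 12 provides none. The gap covers both event types in the competing-risk analysis: survival follow-up begins only once progression is documented, so a progression-free patient has no scheduled ascertainment of progression or of death after month 12.

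Followed literally, the plan gives late figures that either cannot be estimated or rest on whoever happened to be scanned. Unscheduled scans depend on site practice and symptoms, so their timing may carry information about the outcome. Because the trial is meant to provide a signal for a large randomised trial, such figures could be quoted as evidence of durability.

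**Working it through.** **1. How far scheduled follow-up reaches, by time origin** (30.44 days per month)

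- Start of consolidation: 12 months.
- Pre-consolidation CT (section 9.8.8), taken at most 42 days before consolidation: 12 + 42/30.44 = 13.4 months, or 13.8 with the 14-day visit window.
- Induction cycle 1 day 1 (section 9.8.7, time to progression). Shortest path to consolidation: 4 weeks, 27 fractions of 2 Gy (5.4 weeks) and 1 day, which is 9.5 weeks or 2.2 months. Longest: 5 weeks, 1 week between starting chemotherapy and radiation, 37 fractions of 1.8 Gy (7.4 weeks) and 6 weeks, which is 19.4 weeks or 4.5 months. Horizon 14.2 to 16.5 months, or 16.9 with the window.

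No origin reaches 18 months. The scheduled number at risk at 18 and 24 months is 0.

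**2. Footnote 12 against the visit timing**

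For a patient dosed on time, cycle 12 falls 11 × 28 = 308 days after the first consolidation dose. The day-100 visit is then at 408 days, or 13.4 months, already past the cap. The long-term progression follow-up is empty for every on-time completer, although the calendar marks CT there.

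**3. The median**

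Constant hazard (an assumption): median = 12 × ln(0.5)/ln(S12).

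- S12 = 0.559: 14.3 months.
- S12 = 0.699: 23.2 months.
- Historical durvalumab median cited in section 1.1: 16.8 months.

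The median is readable within 12 months only if at least 25 of 49 patients fail by then. Binomial probability with failure rates 0.441 and 0.301: 20% under the null, 0.2% under the alternative. These are PFS figures. Section 12.6.1 asks for median time to progression with death competing, which comes later. If 90% of first events are progressions (an assumption), the probabilities are 7% and 0.03%; if 80%, 1.7% and below 0.01%.

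**4. The plan's sample size, reproduced**

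The documents name no formula, so standard ones were tried. Hazards: λ0 = −ln(0.559)/12 = 0.04847 and λ1 = −ln(0.699)/12 = 0.02984, ratio 0.616. With uniform accrual over A = 18 months and F = 12 further months,

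q = 1 − [exp(−λF) − exp(−λ(A+F))]/(λA),

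so q0 = 0.627 and q1 = 0.459. One-arm exponential test with cube-root transform:

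n = {[1.645·λ0^(1/3)/(3√q0) + 0.842·λ1^(1/3)/(3√q1)] / [λ0^(1/3) − λ1^(1/3)]}²

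= {[0.2524 + 0.1284]/0.05442}² = 48.98, so **49**, with power 0.800. A one-sample log-rank formula gives 48.25, also 49. Tests of a fixed 12-month proportion do not give 49: 74 by normal approximation, 79 by exact binomial.

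**5. The same formulas with every patient cut at 12 months**

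Now q0 = 0.441 and q1 = 0.301.

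| | 12 to 30 months | 12-month cap |
|---|---|---|
| n, cube-root | 49 | 72 (71.33) |
| n, one-sample log-rank | 49 | 74 (73.61) |
| Power at n = 49, cube-root | 0.80 | 0.66 |
| Power at n = 49, log-rank | 0.81 | 0.62 |
| Expected events under the alternative, n = 49 | 22.5 | 14.7 |

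**6. What the calendar would allow without the cap**

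Accrual plus follow-up totals 30 months, and consolidation starts 2.2 to 4.5 months after entry. The share of patients with at least 18 months from consolidation start is (30 − 4.5 − 18)/18 to (30 − 2.2 − 18)/18, or 42% to 54%. For 24 months it is 9% to 21%. The cap, not the calendar, removes the late landmarks.

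**The case against.** The strongest reply is that footnote 12 may be the faulty text, not section 12.6.1. The sample size, the 36-month study duration and the CT marks in the long-term column all fit longer follow-up, and footnote 12 read literally leaves that column empty for on-time completers. This stands. It is why the late landmarks need not simply be deleted, and why the sections must be reconciled.

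A second reply is that footnote 7 keeps recording scans with no end date, so progression data do not stop at 12 months. That is correct: the cap is exact only for scheduled follow-up. But footnote 7 applies where scans happen to be available and sets no timetable. It cannot support a planned 18- or 24-month estimate. That those scans would be a selected subset is an inference, not something the documents state.

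Three stronger readings are tempting, and the documents do not support them:

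- *The median is invalid.* A median that is not attained is reported as not reached. It is unlikely to be attained here, but asking for it is not an error.
- *All curves and estimates should be cut at 12 months at no cost.* That would settle the conflict in favour of the reading that undercuts the stated sample size.
- *The trial is shown to be underpowered.* No formula is named, so the loss of power is conditional on a time-to-event test of the kind that reproduces 49.

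**Conclusion.** Section 12.6.1 is wrong as written on the 18- and 24-month percentages: no patient is scheduled to be under progression follow-up at either time, whichever documented origin is used. This needs no distributional assumption, only on-schedule visits; delayed doses could carry a few on-treatment scans slightly past month 12.

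The statement that the median will probably be unreached rests on constant hazard for the medians of 14.3 and 23.2 months, and on binomial failure counts at n = 49. The link to sample size (72 rather than 49, or power of about 0.66) rests on exponential PFS, uniform accrual and the cube-root test being close to what the sponsor used.

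The affected items are descriptive. The 12-month percentage itself is unaffected.

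**What to change.** Decide first which follow-up is intended, then align the Study Calendar table, footnotes 7 and 12, and sections 9.8.8, 12.3 and 12.6.1.

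- **If the 12-month cap stays:** remove the 18- and 24-month percentages from section 12.6.1, and state that the median is given only if reached and otherwise reported as not reached. Name the test and formula behind the 49 patients in section 12.3, and restate the power under 12-month follow-up. The edit to 12.6.1 is wording; the power statement is not, because the same formula gives about 0.66 at 49 patients, or needs 72.
- **If later landmarks are wanted:** formally extend footnote 12 for all patients, with scheduled progression assessment and ascertainment of death without progression to at least 24 months, and a matching data cut-off. The cost is additional visits and imaging and a later final analysis. If the cut-off stays at 18 + 12 months, state that only about 9% to 21% of patients could have 24 months from consolidation start.

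Under either choice, say how unscheduled scans recorded under footnote 7 enter the analysis.

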### 12.6.2 Analysis Plans for Secondary Objectives

ORR between two time points will be compared, using Chi-square or Fisher exact test for independent samples, and McNemar's Chi-squared test for related or paired samples.

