#### 2.1.2 Secondary Objectives

- Estimate Objective response rate (ORR).

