### 2.2.2 Secondary Endpoints

- Objective response rate (ORR). ORR will be measured using two timepoints, per RECIST 1.1. “ORR1” will be assessed using baseline imaging in comparison to imaging obtained after completion of induction durvalumab and chemoradiation. “ORR2” will be assessed using imaging after completion of induction durvalumab and chemoradiation in comparison to imaging obtained while receiving, and after completion of, consolidation durvalumab.

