#### 9.8.5 Objective Response Rate

Objective response rate (ORR). ORR will be measured using two timepoints, per RECIST 1.1. “ORR1” will be assessed using baseline imaging in comparison to imaging obtained after completion of induction durvalumab and chemoradiation. “ORR2” will be assessed using imaging after completion of induction durvalumab and chemoradiation in comparison to imaging obtained after completion of consolidation durvalumab.

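### The planned test of ORR1 against ORR2 does not serve the aim of estimating response, and its p-value cannot be read as evidence for or against the regimen

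*Combined protocol and SAP*

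**What the plan says.** Section 2.1.2 gives the only secondary objective: "Estimate Objective response rate (ORR"). It names no hypothesis, null value or comparator.

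Section 2.2.2 splits the endpoint in two. ORR1 "will be assessed using baseline imaging in comparison to imaging obtained after completion of induction durvalumab and chemoradiation". ORR2 takes the post-chemoradiation scan as its reference and looks at imaging during consolidation and after it. Section 9.8.5 words the ORR2 follow-up differently: "in comparison to imaging obtained after completion of consolidation durvalumab". Section 12.2.2 likewise refers only to imaging after consolidation.

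Section 12.6.2, the analysis section for this objective, is one sentence. It opens: "ORR between two time points will be compared, using Chi-square or Fisher exact test for independent samples". The rest of the sentence names a second option, which is McNemar for paired data. It does not say which test applies to ORR1 versus ORR2. Section 12.6.4 adds general summary tables, with counts and percentages for categorical efficacy variables. Section 12.5 defines an evaluable set for 12-month PFS only.

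**The concern.** A comparison of two rates is useful when their equality means something. Here the rates cover different treatments, different intervals and different reference scans, and no untreated or historical rate stands beside either. Nothing in the documents says how ORR1 and ORR2 should relate if the regimen works or if it does not.

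There is also a structural limit. A patient whose target lesions have all disappeared by the post-chemoradiation scan has no remaining diameter to shrink, so the decrease that Section 9.5 requires for a partial response cannot occur in ORR2. Success in the first period therefore removes opportunities for response in the second.

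If the sentence is followed, the secondary objective ends in a p-value that readers may take as a finding about induction or consolidation, while the two quantities the objective asks for are reported without an interval and on denominators nobody has fixed.

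**Working it through.** The documents state no expected rate, alpha, power or sample size for this comparison, so there is no planned figure to reproduce. The response counts, correlations and numbers reaching consolidation below are assumptions.

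**Inputs from the documents.** One arm (Section 12.1). 49 patients required and 54 enrolled (Section 12.3). Consolidation is open only to patients without progression who also meet toxicity, performance-status and pneumonitis criteria (Section 3.3). The only response rates quoted are 28.4% with durvalumab and 16% with placebo in the PACIFIC trial (Section 1.1). They serve here as an assumed range for ORR2; these documents do not say which reference scan they used.

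**1. Direction of the p-value.** Pearson chi-square without continuity correction, n = 49 for each rate:

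X² = (p1 − p2)² / [p(1 − p)(2/n)], where p is the pooled rate.

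Hold ORR1 at 24/49 (49.0%):

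| ORR2 | p1 − p2 | pooled p | X² | p-value |
|---|---|---|---|---|
| 8/49 (16.3%) | 16/49 = 0.327 | 32/98 = 0.327 | 11.88 | 0.0006 |
| 14/49 (28.6%) | 10/49 = 0.204 | 38/98 = 0.388 | 4.30 | 0.038 |
| 20/49 (40.8%) | 4/49 = 0.082 | 44/98 = 0.449 | 0.66 | 0.42 |

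The more patients respond during consolidation, the weaker the result. Holding ORR2 at 14/49 and moving ORR1 through 20, 24, 29 and 34 of 49 gives p = 0.203, 0.038, 0.0023 and 0.00005. The p-value depends on both rates and tracks only the gap between them.

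**2. McNemar behaves the same way.** The exact test uses the discordant pairs: responders in the first period only against responders in the second only. With ORR1 at 50%, 49 complete pairs and zero correlation, the expected discordant counts are:

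- ORR2 16%: 49 × 0.50 × 0.84 = 20.6 against 49 × 0.50 × 0.16 = 3.9
- ORR2 28.4%: 49 × 0.50 × 0.716 = 17.5 against 49 × 0.50 × 0.284 = 7.0

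In 20,000 simulated trials per case at two-sided 0.05, the test rejects in 93% and 50% respectively. With 43 pairs the figures are 89% and 44%.

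**3. Independent-samples tests on paired data.** With equal true rates between 28.4% and 50% and 49 pairs, chi-square at nominal 5% rejects in about 9% of simulated trials at correlation −0.3, 5% at 0, 2% at 0.3 and under 1% at 0.5. Its error rate depends on a correlation the plan does not address. McNemar stays at 2 to 3%.

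**4. Selection into the pairs.** Suppose 11 of 54 patients never reach consolidation and none of them responded. ORR1 is 27/54 = 50% among all enrolled but 27/43 = 63% among complete pairs. McNemar would compare ORR2 with the second figure, which is not the ORR1 of the treated cohort.

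**5. What estimation would give.** Exact (Clopper-Pearson) 95% intervals with assumed counts: ORR1 27/54 = 50.0% (36.1 to 63.9). ORR2 12/43 = 27.9% (15.3 to 43.7) among those starting consolidation, or 12/54 = 22.2% (12.0 to 35.6) among all enrolled. The last two show why the denominator has to be written down.

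**The case against.** The strongest defence is that Section 12.6.2 is conditional: independent-samples tests where samples are independent, McNemar where they are paired. On that reading the plan already assigns McNemar to ORR1 versus ORR2, and the chi-square clause is surplus general wording. This is fair. A reader might infer that the plan commits to an independent-samples test on paired data, but the sentence does not go that far. It leaves the choice open, and only one branch fits. McNemar settles the pairing, though not the meaning of the null hypothesis.

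A reader might also infer that response is never estimated. Section 12.6.4 contradicts that, since counts and percentages for efficacy variables would include ORR. What is missing is an interval and an evaluable set.

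Nor do the documents state that the two rates have different denominators. They state none. A difference is a reasonable inference from the consolidation criteria, and McNemar would in any case use the same patients for both rates.

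It would be too strong to say that the p-value carries no information or reflects only tumour shrinkage from chemoradiation. It moves with both rates, and ORR1 includes the effect of induction durvalumab, the experimental component.

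Finally, the consequence is limited. The study is labelled a feasibility study, ORR has no threshold or alpha, and the signal for a larger trial is 12-month PFS. That lowers the severity without giving the comparison a use.

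**Conclusion.** The planned comparison is wrong as written. ORR1 and ORR2 come from one cohort but use different reference scans and treatment periods, so their equality is not a no-effect hypothesis and a p-value against it cannot be read as evidence for or against the regimen. This rests on the endpoint definitions and does not depend on any assumed rate.

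The size of the problem does rest on assumptions. With ORR1 near 50%, raising ORR2 from 16% to 28.4% cuts the chance of a significant McNemar result from 93% to 50% (49 pairs, zero correlation). Over ORR1 from 40% to 70%, that chance runs from 68% to 100% at ORR2 16%, and from 16% to 98% at ORR2 28.4%.

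Separately, the objective of estimation is only partly served: percentages are planned, but no interval is planned and no evaluable set is defined. The change should be made, though it affects neither the primary endpoint nor the decision to go forward.

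**What to change.** In Section 12.6.2, delete the test of ORR1 against ORR2 and replace it with two estimates:

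- ORR1 among all treated patients with measurable disease at baseline, with an exact 95% confidence interval.
- ORR2 among patients starting consolidation with measurable disease on the post-chemoradiation scan, with an exact 95% confidence interval.

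State both evaluable sets in Section 12.5 beside the one for PFS. Reconcile the ORR2 follow-up scans: Section 2.2.2 includes imaging during consolidation, whereas Sections 9.8.5 and 12.2.2 refer only to imaging after it.

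The cost is a few sentences of wording. No extra patients or scans are needed for the two estimates, and the only loss is a p-value with no useful interpretation.

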### 12.6.3 Analysis Plans for Exploratory Objectives

To assess the immune response via peripheral blood immune monitoring through multiple time points of therapy, the patterns of change will be described using descriptive statistics and plots of means (standard deviation) as well as quantiles over time. Additionally, longitudinal data analysis will be employed to calculate the trajectory of change between repeated measures. Various variance-covariance structures will be explored to obtain an efficient model. We will also perform repeated measures ANOVA to test for a time by intervention interaction.

To evaluate the association between outcomes and predictors, controlling for other risk factors, we will perform linear regression analysis for continuous outcome; logistic and ordinal logistic regression analyses for binary and ordinal outcomes, respectively.

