#### 5.4.1 Definition of Dose Limiting Toxicities

The DLT period is through completion of induction durvalumab, chemoradiation, and 2 cycles of consolidation durvalumab. NCI Common Terminology Criteria for Adverse Events (CTCAE) v5 will be used in grading adverse events. A DLT will be defined as:

- Any grade of febrile neutropenia regardless of duration or reversibility  Any Grade 4 immune-mediated adverse event (imAE)  Any grade of immune-mediated neurotoxicity.
- Grade  $\geq$  3 colitis
- Grade 3 non-infectious pneumonitis irrespective of duration
- Grade 2 pneumonitis that does not resolve to  $\leq$  Grade 1 within 3 days of the initiation of maximal supportive care
- Grade 3 imAE, excluding colitis or pneumonitis, that does not downgrade to Grade 2 within 3 days after onset of the event despite optimal medical management including systemic corticosteroids or does not downgrade to  $\leq$  Grade 1 or baseline within 14 days
- Grade 3 liver transaminase elevation with concurrent total bilirubin  $> 2 \times$  ULN  Grade  $\geq$  3 non-imAE, except for the exclusions listed below

The following conditions are excluded from the DLT definition:

- Grade 3 fatigue lasting  $\leq$  7 days
- Grade 3 endocrine disorder (thyroid, pituitary, and/or adrenal insufficiency) that is managed with or without systemic corticosteroid therapy and/or hormone replacement therapy and the subject is asymptomatic
- Grade 3 inflammatory reaction attributed to a local antitumor response (eg, inflammatory reaction at sites of metastatic disease, lymph nodes, etc)
- Concurrent vitiligo or alopecia of any AE grade
- Grade 3 infusion-related reaction (first occurrence and in the absence of steroid prophylaxis) that resolves within 6 hours with appropriate clinical management
- Grade 3 or 4 neutropenia that is not associated with fever or systemic infection that improves by at least 1 grade within 3 days.
- Grade 3 or 4 lymphopenia
- Grade 3 thrombocytopenia that is not associated with clinically significant bleeding that requires medical intervention and improves by at least 1 grade within 3 days
- Isolated Grade 3 electrolyte abnormalities that are not associated with clinical signs or symptoms and are reversed with appropriate maximal medical intervention within 3 days
- Transient asymptomatic laboratory abnormalities that do not require hospitalization

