### 8.2.1 Serum

Specimens for serum will be collected prior to C1D1 induction durvalumab; prior to C1D1 consolidation durvalumab; and at 8 weeks after consolidation durvalumab (prior to Cycle 3) for immune monitoring analysis. All specimens should be collected prior to drug administration.

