## 11.2 Reporting

### 11.2.1 Adverse Events

- AEs will be recorded from time of signed informed consent until 90 days after discontinuation of study drug(s) or until a new anti-cancer treatment starts, whichever occurs first.
- AEs will be recorded regardless of whether or not they are considered related to the study drug(s).
- All AEs will be recorded in the subject's medical record and on the appropriate study specific eCRF form within the EDC system.

- AEs considered related to study drug(s) will be followed until resolution to  $\leq$  Grade 1 or baseline, deemed clinically insignificant, and/or until a new anti-cancer treatment starts, whichever occurs first.

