#### 12.2.3 Correlative/Exploratory Endpoints

Data analysis for the correlative/exploratory objectives are descriptive and exploratory. Refer to Sections 12.6.3 and 12.6.5, below, for details of analysis plan for the correlative and exploratory endpoints.

- Correlation of outcomes and toxicity based upon tumor and immune cell PD-L1 status in baseline tumor biopsy prior to therapy.
- Correlation of toxicity based upon type of chemotherapy administered.

Patients receiving different chemotherapeutic agents will be analyzed together for toxicity, with exploratory analysis of toxicity related to different chemotherapeutic regimens.

- Correlation of outcomes based upon tumor mutation burden in baseline tumor biopsy prior to therapy
- Assessment of immune response via peripheral blood immune monitoring through multiple timepoints of therapy
- Correlation of immune response with outcomes in terms of disease control and toxicity
- Correlation of tumor immune score via quantitative multiplex tumor biopsy assay with clinical outcomes
- Exploration of immune response signal to indicate further exploration of a treatment schedule in a larger trial
- Collection of microbiome samples to correlate with outcomes and toxicity

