Based on the severity of the imAE, durvalumab should be withheld and corticosteroids administered. Upon improvement to Grade  $\leq 1$ , corticosteroid should be tapered over  $\geq 28$  days. More potent immunosuppressive agents such as TNF inhibitors (e.g., infliximab) should be considered for events not responding to systemic steroids. Alternative immunosuppressive agents not listed in this guideline may be considered at the discretion of the investigator based on clinical practice and relevant guidelines. With long-term steroid and other immunosuppressive use, consider need for *Pneumocystis jirovecii* pneumonia (PJP, formerly known as *Pneumocystis carinii* pneumonia) prophylaxis, gastrointestinal protection, and glucose monitoring.

Dose modifications of study drug/study regimen should be based on severity of treatmentemergent toxicities graded per NCI CTCAE version in the applicable study protocol.

AE Adverse event; CTC Common Toxicity Criteria; CTCAE Common Terminology Criteria for Adverse Events; imAE immune-mediated adverse event; NCI National Cancer Institute; NCCN National Comprehensive Cancer Network; ESMO European Society for Medical Oncology

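### Exploratory blood-marker regressions do not tie on-treatment samples to an outcome window, so toxicity before the draw can pass as its consequence; no model for censored PFS is named

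*Combined protocol and SAP*

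**What the plan says.** The exploratory endpoints in Section 12.2.3 include "Assessment of immune response via peripheral blood immune monitoring through multiple timepoints of therapy" and "Correlation of immune response with outcomes in terms of disease control and toxicity". On-treatment samples are therefore part of the predictor.

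Blood is drawn three times (Section 7, footnote 9; Sections 8.2.1 to 8.2.3): before induction, before the first consolidation dose, and "at 8 weeks after consolidation durvalumab (prior to Cycle 3) for immune monitoring analysis". Under Section 11.2.1, adverse events are recorded from signed consent. Under Section 12.5, PFS runs from the imaging done after chemoradiation and before consolidation.

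For associations of outcomes with predictors, Section 12.6.3 states "we will perform linear regression analysis for continuous outcome; logistic and ordinal logistic regression analyses for binary and ordinal outcomes, respectively". It names no sample, no outcome window and no time-to-event model. Section 12.2.3 also points to a Section 12.6.5, which does not appear in the text available; 12.6.4 is followed by 12.7.

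Appendix A links toxicity to later treatment: "Based on the severity of the imAE, durvalumab should be withheld and corticosteroids administered". The taper after improvement lasts at least 28 days.

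**The concern.** A regression of any toxicity on the week-8 immune value would use a predictor measured after part of its outcome. If an earlier immune-mediated event, or the steroids given for it, moved the marker, the association runs from toxicity to marker but would be read the other way. The pre-consolidation sample has the same weakness for toxicity during induction and chemoradiation.

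The second gap concerns the model. The synopsis asks for PFS by baseline PD-L1 status. Linear, logistic and ordinal regression do not use censored follow-up times correctly. The survival methods in Section 12.6.1 are assigned elsewhere: competing-risk regression to study arm versus historical control, and log-rank and Cox to overall survival between groups.

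What is at stake is the immune signal, which Section 2.1.3 intends as a guide to exploring a treatment schedule in a larger trial.

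**Working it through.** **Which markers are exposed**

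| Marker | Drawn | Can recorded toxicity precede it? |
|---|---|---|
| PD-L1, TMB, tumor immune score, stool | Before treatment | Not on-treatment toxicity |
| Blood sample 1 | Before induction | Not on-treatment toxicity |
| Blood sample 2 | Before consolidation cycle 1 | Yes: induction and chemoradiation |
| Blood sample 3 | Before consolidation cycle 3 | Yes: also the first two consolidation cycles |

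**Size for toxicity.** The plan gives no sample size, power or error rate for these regressions, so there is no plan figure to reproduce. I use n = 49 from Section 12.3. Assumptions, none of them in the documents: 25% of patients have toxicity before week 8, 15% have toxicity after it, independently, and the marker predicts nothing. Early toxicity shifts the week-8 marker by d standard deviations. The marker is compared between patients with and without any toxicity, using a two-sided t-test at 5%.

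| Early-toxicity patients who give sample 3 (assumed) | d = 0 | d = 0.5 | d = 1.0 |
|---|---|---|---|
| All | about 4% to 5% | about 20% | about 58% |
| Half | about 5% | about 12% | about 30% |
| A quarter | about 5% | about 8% | about 15% |
| Only post-draw toxicity counted, patients with earlier toxicity set aside | about 5% | about 5% | about 5% |

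A second set of assumptions takes total toxicity at 24%, close to the 24.2% immune-mediated rate quoted for the historical durvalumab arm in Section 1.1. With 25% to 75% of it before the draw and shifts of 0.5 to 1.0 SD, the test rejects in 6% to 55% of trials, and in 4% to 5% with post-draw counting. When 75% of toxicity is early, about one simulated trial in five has fewer than two later events and cannot be tested.

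**Events left after the draw** (first set of assumptions)

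- Patients with earlier toxicity set aside: 49 × 0.75 × 0.15 = 5.5.
- Patients with earlier toxicity kept: 49 × 0.15 = 7.4.
- A model with the marker, prior immune-mediated event and steroid use has three slopes: 7.4 / 3 = about 2.5 events per slope.

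**PFS and the week-8 sample.** Assume exponential PFS, with 8 weeks = 56 / 30.44 = 1.84 months and S(8 weeks) = p^(1.84/12), where p is 12-month PFS.

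| 12-month PFS (Section 12.3) | S(8 weeks) | Events of 49 before week 8 | 12-month PFS given event-free at week 8 |
|---|---|---|---|
| 55.9% | 0.915 | 49 × 0.085 = 4.2 | 0.559 / 0.915 = 61.1% |
| 69.9% | 0.947 | 49 × 0.053 = 2.6 | 0.699 / 0.947 = 73.8% |

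About 45 to 46 of 49 patients remain at the landmark. Fewer events than this would actually be dated before week 8, because the first scheduled scan in consolidation is at about three months (Section 7, footnote 7). In a null simulation restricted to sampled patients, with PFS still counted from the earlier start, the marker test rejected in 5.1% of trials. Guaranteed event-free time raises the level of PFS in this group but does not by itself create a false association.

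**The case against.** **The plan does not order the faulty analysis.** True. Section 12.6.3 is silent on sample and window, and a careful analyst could choose correctly. The gap is an omission that permits the wrong choice.

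**The inflation rests on assumptions, and sampling may limit it.** This stands in part. Section 3.3 requires recovery to below Grade 2 and no pneumonitis before consolidation, Section 6.2 ends therapy after an interruption of six weeks or more, and Appendix A generally ties resumption to completing the steroid taper. Many patients with early toxicity may never give sample 3. That lowers the figures to about 8% to 12% at 0.5 SD and 15% to 30% at 1.0 SD. It does not bring them to 5%, and it makes the sampled group a selected one.

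**A reader might infer that PFS events also precede and cause the marker values.** The documents do not support this. Sample 2 is taken essentially at the PFS start, in patients who have not progressed. Sample 3 normally precedes the first scheduled scan. The exceptions are few, such as patients treated past unconfirmed progression under Section 6.2. What remains is guaranteed event-free time, without inflation of the null error.

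**A reader might treat the dose-limiting toxicity window as the correlative outcome.** It is a run-in stopping rule for the first 10 patients (Section 5.4), not the toxicity outcome of these regressions.

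**The analyses are descriptive and exploratory, and depend on funding.** Correct, and this limits the weight of the point. It excuses low power, but not a predictor measured after its outcome.

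**Conclusion.** This is a cheap improvement confined to exploratory analyses. For blood samples 2 and 3, Section 12.6.3 allows toxicity that preceded the draw to be analysed as if the marker predicted it. The false-positive rate at nominal 5% is roughly 8% to 58% for assumed shifts of 0.5 to 1.0 SD, depending also on the assumed early-toxicity share and on how many early-toxicity patients are sampled. With no shift there is no inflation, and the documents give no size for it.

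The missing model for censored PFS is a separate gap. It also reaches pre-treatment markers such as PD-L1, which the timing problem does not touch. It would be wrong to conclude that the biomarker programme as a whole is compromised, or that the primary comparison is.

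**What to change.** Add to Section 12.6.3:

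- For blood samples 2 and 3, relate the sample only to toxicity with onset after that draw. State how patients with earlier toxicity are handled; the check above set them aside. Report toxicity before the draw separately and descriptively.
- Use Cox regression with Kaplan-Meier display for biomarker-PFS associations. For the week-8 sample, start PFS at that draw among patients then event-free.
- Do not put prior immune-mediated events and steroid use into the model as covariates. With about 5 to 7 later events expected under the assumptions above, the data cannot carry them. Show them descriptively or in a sensitivity analysis.

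The cost is SAP wording and fewer events in the later-sample analyses, in some scenarios too few for any test. The sponsor should confirm that adverse event onset dates, draw dates and steroid dates are captured, since Section 5.5.1 leaves the recording of medication dates optional when changes occur. No visit, sample or primary analysis changes.
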